#### 6.16.2.2. Clinical Worsening based on the NIAID Scale

Clinical worsening is defined as the proportion (percentage) of participants with any worsening on the NIAID ordinal scale from baseline to the end of the Evaluation Period. Treatment group comparisons will be analyzed using logistic regression, if there are sufficient data available.

Missing data will be imputed using the NRI method as described in Section 6.3.3.

#### 6.16.2.3. Time to Hospitalization from first positive SARS-CoV-2 test

Time to Hospitalization is defined (in days) as:

*(First study day when hospitalized status is changed to “Yes” – Date of first positive SARS-CoV-2 test +1)*

Only patients who have at baseline or later develop SARS-CoV-2 infection will be included in the analysis. If a patient has not been admitted to the hospital or ICU by completion or early discontinuation of the evaluation period, the patient will be censored at the date of their last visit during the evaluation period.

Time to hospitalization will be evaluated during the study evaluation period only and will be summarized by treatment group, and listed for the Prevention and Treatment populations. Cox proportional hazard methodology will be used.

Time to hospitalization may be presented graphically.

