8.2.4. Hospitalization events

If a participant is admitted to the hospital, the participant will remain in the study and follow the procedures outlined in the SoA. Hospitalization is defined as ≥ 24 hours of acute care.

The date of hospitalization events will be recorded in the CRF and includes

- hospitalization
- emergency room visit
- intensive care unit admittance

- extended care facility admittance, and
- discharge for any of the above.

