**Table PYAD.6.2. Definition of Study Period Time Intervals**

Study Period	Interval Start Definition	Interval End Definition
Screening: All patients who sign informed consent are considered as entering the Screening Period.	Informed consent date	Prior to the start of Evaluation Period.
Evaluation Period: All patients who are randomized to the study are considered as entering the Evaluation Period.	At the start of study drug administration date/time following randomization. For patients who are randomized but not dosed, the Evaluation Period starts on the date of randomization.	The minimum of Evaluation Period discontinued date, study discontinuation date, or first Follow-Up visit date.
Follow-Up: All patients who had a follow up visit are considered as entering follow-up period.	After the Evaluation Period ends.	The maximum of the last study visit date or study disposition date.

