#### **6.10.3.4. Hospitalization or Death Due to COVID-19 by Day 57**

The proportion of patients who experience hospitalization or death due to COVID-19 during the Evaluation Period will be summarized for participants in the Prevention population. In addition, the number of patients that experience hospitalization or death due to COVID-19 will be analyzed using logistic regression to compare each study intervention versus placebo, if there are sufficient data available. Statistical comparisons will be done using a logistic regression model. The model will include treatment, facility, role within the facility (resident vs staff) and sex as fixed effects. Missing data will be imputed using the NRI method as described in Section 6.3.3.

A listing of hospitalization status during the Evaluation Period will be created.

As an exploratory analysis, this analysis will be repeated on participants in the Treatment populations. Additionally, at each End of Evaluation Database Lock, the number of patients who are hospitalized or have died due to COVID-19 anytime after randomization will be analyzed to compare each study intervention versus placebo in the Prevention and Treatment populations, if there are sufficient data available.

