#### **6.16.2.4. Time to Admission to ICU from first positive SARS-CoV-2 test**

Time to ICU is defined (in days) as:

$$(First\ study\ day\ when\ ICU\ status\ is\ changed\ to\ "Yes" - Date\ of\ first\ positive\ SARS-CoV-2\ test +1)$$

Only patients who have at baseline or later develop SARS-CoV-2 infection will be included in the analysis. If a patient has been admitted to the hospital or ICU by completion or early discontinuation of the evaluation period, the patient will be censored at the date of their last visit during the evaluation period.

Time to ICU will be evaluated during the study evaluation period only and will be summarized by treatment, and listed for the Prevention and Treatment populations. Cox proportional hazard methodology will be used.

Time to ICU may be presented graphically.

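### Exploratory time to hospitalization or ICU admission counts the first stay on study for any cause, so an unrelated stay before the first positive test gives a time of zero or less and displaces a later COVID-19 admission

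*SAP*

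**What the plan says.** SAP 6.16.2.3 gives the time as "First study day when hospitalized status is changed to “Yes” – Date of first positive SARS-CoV-2 test +1". It sets the analysis set this way: "Only patients who have at baseline or later develop SARS-CoV-2 infection will be included in the analysis". The window is stated as "Time to hospitalization will be evaluated during the study evaluation period only", and results are to be "summarized by treatment group, and listed for the Prevention and Treatment populations. Cox proportional hazard methodology will be used". SAP 6.16.2.4 repeats the formula for ICU admission.

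Three other places bear on the reading:

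- SAP Table PYAD.6.2 starts the Evaluation Period, for dosed participants, as follows: "At the start of study drug administration date/time following randomization". Hospital days therefore count from Day 1, before any post-baseline infection.
- Protocol 8.2.4 sets no cause: "Hospitalization is defined as ≥ 24 hours of acute care".
- Where the SAP wants a COVID-19 restriction, it writes one. SAP 6.10.3.4 analyses "The proportion of patients who experience hospitalization or death due to COVID-19 during the Evaluation Period", and SAP 6.10.3.5 and 6.16.1.6 are also limited to COVID-19.

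Neither 6.16.2.3 nor 6.16.2.4 has a rule for an earlier stay, a repeat stay, or a time of zero or less.

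**The concern.** Members of the Prevention populations are RT-PCR negative at baseline, so each first positive among them comes after time already spent on study. A participant can be admitted for something unrelated, return to the facility, and test positive weeks later. Read literally, the formula picks the earlier stay as the event and places it before the time origin. A Cox model that starts the clock at the first positive test has no valid place for such a time.

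Two things follow. The participant carries an event that did not follow infection. A COVID-19 admission that did follow it is not used, because only the first stay counts. The statistician must then drop, recode or replace the record without a prespecified rule, in an analysis likely to have few events.

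**Working it through.** The documents state no figure for this endpoint, so there is nothing to reproduce. The check applies the formula directly.

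**Formula.** T = H − P + 1, where H is the study day of the first hospitalized status and P is the study day of the first positive test (SAP 6.16.2.3). The scheduled post-baseline swabs in the Evaluation Period for the Prevention populations fall on Days 8, 15, 22, 29, 36, 43, 50 and 57 (Protocol 1.3.1).

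**Worked case.** Unrelated stay Day 12, first positive Day 29, COVID-19 admission Day 33.

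- As written: 12 − 29 + 1 = −16.
- As intended: 33 − 29 + 1 = 5.

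**Where the formula fails.** Admission on the day of the positive gives T = 1. Admission the day before gives T = 0. Anything earlier is negative.

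| First positive | Earlier admission days giving T ≤ 0 | Lowest T (admission Day 1) |
|---|---|---|
| Day 8 | 7 | 1 − 8 + 1 = −6 |
| Day 29 | 28 | 1 − 29 + 1 = −27 |
| Day 57 | 56 | 1 − 57 + 1 = −55 |

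A participant positive at baseline always has T ≥ 1, because inpatients are excluded at entry (Protocol 5.2, criterion 10). For that group only the missing cause restriction remains.

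**Size, by assumption.** Let h be the weekly rate of unrelated admission, with first positives spread evenly over the eight swabs. The share of post-baseline infected participants with an earlier stay is the mean of 1 − (1 − h)^w over w = 1 to 8:

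- h = 0.5%: 0.022
- h = 1%: 0.044
- h = 2%: 0.086

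If earlier stays are independent of later admission, the same 2% to 9% is the share of true post-infection admissions displaced. Parametrised instead by an assumed 8-week risk r of an unrelated stay, with daily hazard −ln(1 − r)/56, r = 2%, 5% and 10% give 1.1%, 2.8% and 5.7% with T ≤ 0.

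**COVID-19 admissions before the first study positive.** Protocol 1.3.1 does not require swabs during a hospital stay, and its footnote says local results are not collected in the eCRF while the participant is in hospital. A COVID-19 admission on Day 12 with a first study positive on Day 22, after discharge, gives 12 − 22 + 1 = −9. A rule that only requires admission on or after the first positive would discard this genuine event.

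**The case against.** The best defence is that the section heading fixes the origin at the first positive test, and SAP 6.1.3 already defines every interval as end date minus start date plus 1. On that view an admission before the origin is outside what the section describes. Part of this stands. The intent is clear, and subtracting a date from a study day is loose wording that 6.1.3 resolves. A reader might infer a separate units error, but the documents do not support one. However, 6.1.3 says how to compute an interval, not which stay ends it, and the formula names the first.

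Any-cause admission may also have been deliberate, since SAP 6.16.2.5 names no cause either. Even so, the condition that the stay follow the positive test would still be needed.

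A reader might infer that Cox software deletes such records. SAP 6.1 permits SAS or R and does not say how non-positive times are treated, so that cannot be assumed. It does not change the result: whether the record is dropped or ranked as the earliest event, the later COVID-19 admission is unused.

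It is also fair that participant-level values are listed, so a negative time would be seen. Seeing it does not supply a rule for handling it.

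**Conclusion.** The definition is wrong as written in both sections, and the importance is low. These are exploratory analyses that the protocol does not define (SAP 6.16.2), and they lie outside the testing scheme in SAP 6.5.

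A reader might infer that the trial's hospitalization results in general are compromised. They are not. COVID-19 hospitalization or death (6.10.3.4), COVID-19-related deterioration (6.10.3.5) and duration of COVID-19 hospitalization (6.16.1.6) are limited to COVID-19 and do not use this formula. No primary, key secondary or other secondary result changes.

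The zero and negative times are certain arithmetic; their frequency is not known. The 2% to 9% rests on assumed weekly rates of 0.5% to 2%, an even spread of first positives, and independence between earlier and later stays. Staff are enrolled too, with a minimum of only 300 residents, so the upper end may not describe the whole population. If frailer residents have both kinds of stay more often, the displaced share would be larger.

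A reader might also divide 0.022 to 0.086 by an assumed 15% admission rate after infection, get 0.15 to 0.57, and conclude that 15% to 57% of true admissions are lost. That quotient compares all participants with an earlier stay to true events, and most of those participants would have no COVID-19 admission to displace. On the same assumptions the displaced admissions are 0.15 × 0.022 = 0.3% to 0.15 × 0.086 = 1.3% of infected participants.

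**What to change.** In SAP 6.16.2.3 and 6.16.2.4:

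- Define the event as the first COVID-19-related hospitalization (or ICU admission) starting on or after the date of first positive test, with time equal to admission date minus first-positive date plus 1.
- Ignore earlier stays not related to COVID-19.
- Count a COVID-19-related admission that starts before the first study positive as an event at day 1, whether the positive is found during the stay or after discharge.

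The cost is about a sentence per item in each section. Hospitalization and ICU admission dates are already recorded in the CRF (Protocol 8.2.4), test dates come with the swab results, and attribution of hospitalization to COVID-19 is already needed for SAP 6.10.3.4 and 6.10.3.5. No new data collection is implied for hospitalization; the sponsor should confirm that the same attribution can be carried to ICU admissions. While 6.16.2.4 is open, its censoring sentence should be corrected too: it censors those who have been admitted, the reverse of 6.16.2.3.

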
 Compare the incidence of SARS-CoV-2 infection Compare the frequency of hospitalization or death due to COVID-19 Characterize clinical status for participants. Compare the mortality due to COVID-19 	
 Cumulative incidence of SARS-CoV-2 infection defined as the detection of SARS-CoV-2 by RT-PCR Proportion of participants who are hospitalized or have died due to COVID-19 Proportion (percentage) of participants who experience these events: 
 COVID-19 related hospitalization (defined as ≥ 24 hours of acute care), COVID-19 related emergency room visit, or death Proportion of participants who die due to COVID-19 (according to the investigator)
Exploratory	
[time frame for endpoint evaluation: 8 weeks from randomization]	

 Compare time to improvement to mild severity symptoms in participants who develop moderate or worse severity^a COVID-19 Characterize COVID-19 illness and severity according to NIAID ordinal scale(s) Characterize SARS-CoV-2 viral endpoints in those participants that become RT-PCR positive Characterize emergence of viral resistance to LY3819253 Compare the duration of hospitalization due to COVID-19 	
 Time to improvement to mild severity^a Worst score on NIAID ordinal scale(s) Proportion of participants that achieve SARS-CoV-2 clearance within 1, 2, or 3 weeks of positive RT-PCR Time to SARS-CoV-2 clearance Comparison from the first positive sample to at least the last positive sample Cumulative days of hospitalization in those who are hospitalized due to COVID-19

Abbreviations: COVID-19 = coronavirus disease – 2019; NIAID = National Institute of Allergy and Infectious Diseases; RT-PCR = reverse transcription – polymerase chain reaction; SARS-CoV-2 = severe acute respiratory syndrome coronavirus 2.

^a As defined in [Table 1](#).

Treatment Population Exploratory Objectives and Endpoints Participants positive at baseline for SARS-CoV-2 RT-PCR and negative at baseline for serology Comparison Groups: Placebo vs LY3819253 4200 mg [time frame for endpoint evaluation: 8 weeks from randomization]	
Objectives	Endpoints

 Compare the frequency of hospitalization or death due to COVID-19 	
 Proportion of participants who are hospitalized or have died due to COVID-19

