9.4.7. Exploratory Endpoints

As exploratory analyses, the primary and secondary analyses may be repeated on the Treatment populations and on all participants who are in either the Prevention or Treatment populations in Part 1 and 2.

Additional exploratory analyses for Part 1 and Part 2 may include

- time to improvement of COVID-19 disease to mild severity, in the subset of the participants who have at baseline, or develop, moderate or worse COVID-19
- worst score according to NIAID ordinal scale(s)
- examination of virology for participants who become SARS-CoV-2 positive,
- examination of viral resistance to each study intervention,
- duration of hospitalization in participants who are hospitalized due to COVID-19, and
- subgroup analyses of primary and key secondary endpoints within residents versus staff.

For Part 3, exploratory analyses are listed in Section 3.

Additional exploratory analyses on Part 3 may be conducted.

Details on these analyses will be described in the SAP.

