#### 6.1.1. Analysis Populations

Patient populations are defined in [Table PYAD.6.1](#) along with the analysis they will be used to conduct. The treatment groups and inferential comparisons described in [Table PYAD.6.1](#) will be used unless otherwise specified. Also, unless otherwise specified, for all populations/analysis, patients will be analyzed according to the treatment to which they were assigned.

If enrolling to a placebo-controlled trial is challenged by an effective medication becoming available for prevention of COVID-19 and SARS-CoV-2, then the placebo arm may be dropped in Part 2.

Throughout the document, the term “the Prevention populations” will be used to describe both the Part 1 Prevention and Part 2 Prevention populations. Analyses on the Prevention populations will be conducted on each Prevention population separately. The terms “the Treatment populations” and “the Safety populations” are defined similarly, including those populations from Part 3 of the study.

Table PYAD.6.1. Analysis Populations

Population	Description
Entered	
Definition: All patients who signed informed consent.
 
Purpose: Used for disposition analysis.
 
Treatment Groups: None
 
Inferential Comparisons: None

Enrolled/Intent-to-Treat (ITT)	
Definition: All participants assigned to treatment, regardless of whether they take any doses of study treatment, or if they took the correct treatment. Patients will be analyzed according to the treatment group to which they were assigned.
 
Purpose: Used for disposition, demographic, and safety analyses.
 
Treatment Groups (Short Label):
 
 
Part 1: 4200 mg LY3819253 (4200 LY) and placebo (Pbo)
 
Part 2: 700 mg LY3819253, 350 mg LY3819253 + 700mg LY3832479, and placebo
 
 
Inferential Comparisons: LY versus placebo

Part 1 Prevention	
Definition: All participants in the Enrolled/Intent-to-Treat population in Part 1 who are SARS-CoV-2 RT-PCR negative and serology negative at baseline.
 
Purpose: Used for efficacy and health outcomes analyses.
 
Treatment Groups (Short Label): 4200 mg LY3819253 (4200 LY) and placebo (Pbo)
 
Inferential Comparisons: LY versus placebo

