#### 6.16.1.6. Duration of Hospitalization

Treatment comparisons of the mean DOH (in days) due to COVID-19 will be compared between each study intervention and placebo using a nonparametric rank-sum test (such as Mann-Whitney or van Elteren test) adjusting for facility and for the randomization stratification factors. This comparison will be made on the Prevention and Treatment populations.

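### In the Prevention populations, time to hospitalization or ICU is compared only among the infected and hospital days only among the hospitalized, so these are not randomized comparisons and can hide, reverse or exaggerate a benefit

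*SAP*

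**What the plan says.** SAP 6.16.2.3 defines time to hospitalization as running from the first positive SARS-CoV-2 test and restricts who enters: "Only patients who have at baseline or later develop SARS-CoV-2 infection will be included in the analysis". The result is "summarized by treatment group, and listed for the Prevention and Treatment populations. Cox proportional hazard methodology will be used". SAP 6.16.2.4 uses the same restriction, time origin and method for ICU admission.

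For hospital stay, SAP 6.16.1.6 says: "Treatment comparisons of the mean DOH (in days) due to COVID-19 will be compared between each study intervention and placebo", by a rank-sum test adjusted for facility and the stratification factors, and "This comparison will be made on the Prevention and Treatment populations". That section does not itself limit the comparison to hospitalized participants. The limit comes from the endpoint definition in Protocol Section 3 (Part 1 exploratory objectives), "Cumulative days of hospitalization in those who are hospitalized due to COVID-19". It recurs in Protocol 9.4.7 and SAP Tables PYAD.4.3 to 4.6.

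The Part 1 Prevention population consists of participants "who are SARS-CoV-2 RT-PCR negative and serology negative at baseline" (SAP 6.1.1). Part 2 Prevention carries the same condition.

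These are planned as treatment comparisons. SAP Table PYAD.6.3 assigns Cox models to treatment comparisons, and SAP 6.1.4 has the hazard ratio and log-rank test reported. SAP 6.5 puts all other analyses at two-sided 0.05 without multiplicity adjustment. No caveat or descriptive-only label is attached.

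**The concern.** In the Prevention populations nobody is known to be infected at randomization. Becoming infected, and then being hospitalized, are things the drug is meant to change; infection by Day 29 is itself a key secondary endpoint (SAP 6.10.3.2). Selecting on either one compares the people in whom the drug failed with a broader set of placebo participants. Randomization no longer balances the two groups, and the time origin is itself a post-randomization event.

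A hazard ratio or p-value from such a comparison mixes the effect of the drug after infection with differences in who got infected. A real reduction in hospitalization could appear as no effect or as harm. Equally, the analysis could suggest a post-infection benefit that does not exist. These results would stand in the same report as the randomized endpoints, with no mark to distinguish them.

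**Working it through.** **Inputs from the documents.** Part 1: two-sided 0.05, 90% power, placebo 8-week risk 4.0% for moderate or worse COVID-19, 33 events (SAP 5.2), 1:1 allocation (Protocol 6.3). The risk ratio of 0.33 is stated for the primary and key secondary endpoints, so it covers infection. The documents do not give a placebo infection or hospitalization risk, an effect on hospitalization, effects by risk group, or lengths of stay. Values for these below are assumptions.

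**1. The plan's own figure.** Schoenfeld: 4 × (1.960 + 1.282)² / (ln 0.33)² = 34.2 events. Converting risks to hazards, HR = ln(1 − 0.0132)/ln(1 − 0.04) = 0.3255, which gives 33.4. The stated 33 is consistent with a planning ratio of 0.33.

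**2. What the infected-only comparison estimates.** If every COVID-19 hospitalization occurs in someone counted as infected, the risk among the infected in each arm is P(hospitalized)/P(infected). The ratio between arms is therefore RR(hospitalization)/RR(infection).

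| RR(infection) | RR(hospitalization), all participants | Ratio among infected |
|---|---|---|
| 0.33 | 0.33 | 1.00 |
| 0.33 | 0.50 | 1.52 |
| 0.33 | 0.70 | 2.12 |
| 0.70 | 0.33 | 0.47 |

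Whenever the drug prevents infection, the ratio among the infected lies above the all-participant ratio; at RR(infection) 0.33 it is 1/0.33 = 3.03 times as large.

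**3. Two-group illustration.** Assume half of placebo infections are in low-risk people (2% hospitalized), half are in frail people (20%), and the drug does nothing after infection. Placebo risk among the infected: 0.5 × 0.02 + 0.5 × 0.20 = 0.110.

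- Drug prevents 80% of low-risk and 40% of frail infections: (0.1 × 0.02 + 0.3 × 0.20)/0.4 = 0.155. Ratio among infected 0.155/0.110 = 1.41; all participants 0.062/0.110 = 0.56.
- Efficacies swapped: (0.3 × 0.02 + 0.1 × 0.20)/0.4 = 0.065. Ratio among infected 0.065/0.110 = 0.59; all participants 0.026/0.110 = 0.24.
- Equal efficacy in both groups: ratio among infected 1.00.

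The true post-infection effect is nil in all three cases, yet the conditional ratio runs from 0.59 to 1.41.

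**4. Cox model in the infected, by simulation.** Assume placebo infection 10% and hospitalization 2%. With RR 0.33 for all infections, the all-participant RR is 0.33 and the Cox hazard ratio in the infected is 0.99. With RR 0.33 for infections that would stay out of hospital and 0.50 for those that would not, the figures are 0.50 and 1.42.

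**5. Hospital days.** Assume half of placebo stays last 4 days and half 14, mean 9.0. If the drug prevents 80% of short and 30% of long stays, the mean among the hospitalized is (0.10 × 4 + 0.35 × 14)/0.45 = 11.8 days, while total days per randomized participant fall to 5.3/9.0 = 0.59 of placebo. With those efficacies swapped, the mean is (0.35 × 4 + 0.10 × 14)/0.45 = 6.2 days and the total falls to 2.8/9.0 = 0.31.

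**The case against.** The strongest reply is that the trial already answers the hospitalization question in randomized groups. SAP 6.10.3.4 (hospitalization or death due to COVID-19) and 6.10.3.5 (deterioration) are secondary analyses in the whole Prevention population. SAP 6.16.2.5 compares proportions hospitalized, in ICU and ventilated there at Day 57. The conditional analyses are exploratory and outside the testing scheme, and a reader who saw them contradict the all-participant results could tell that something was off. This stands and keeps the consequence small. It does not cover hospital days, which have no all-randomized comparison.

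A second reply is that the size and direction are assumed. That also stands. The documents give no split of efficacy by frailty. Protocol 2.2 expects the drug to lessen severity, and Protocol 2.3 cites interim data suggesting fewer hospitalizations in treated patients. If hospitalization after infection were halved in the first case of the illustration, the conditional ratio would be 0.0775/0.110 = 0.70, in favour of the drug. It would still differ from the all-participant 0.031/0.110 = 0.28.

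A third reply is that severity among breakthrough infections is of real interest. It is, but without further assumptions the comparison does not isolate what the drug does after infection, so a descriptive summary is as far as it supports.

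**Conclusion.** The point holds as a low-severity matter of analysis choice. In the Prevention populations the planned Cox comparisons for hospitalization and ICU, and the rank test on hospital days, condition on outcomes of treatment. They have no randomized interpretation whatever direction the error takes. For hospital days the same applies in the Treatment populations, because hospitalization follows randomization there too.

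The size depends on quantities the documents do not give. If the planning ratio of 0.33 also applied to hospitalization, a drug preventing two thirds of hospitalizations would show a ratio of about 1.0 among the infected. The range 0.59 to 1.41 belongs to the assumed illustration.

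Three stronger readings are tempting and are not supported:

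- That an effective drug should be expected to look harmful. Reversal needs RR(hospitalization) to exceed RR(infection), which the documents neither state nor imply.
- That the facility-adjusted rank test would have nothing to compare because almost every stratum holds one person. Neither the number of facilities nor the expected number of hospitalizations is given, and SAP 6.16.1.6 names its tests only as examples. Sparse strata are possible, but only as an assumption.
- That all the infected-only analyses are flawed. In the Treatment populations infection is a baseline condition, so time to hospitalization and time to ICU keep the randomized groups.

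**What to change.** - **Prevention populations, SAP 6.16.2.3 and 6.16.2.4:** analyse time from randomization to COVID-19-related hospitalization, and to ICU admission, in all participants, censored at Day 57 or last contact. State the rule for death: a competing event or part of a composite. The limit to COVID-19-related admissions is needed because 6.16.2.3 currently counts any change to hospitalized status.
- **Prevention and Treatment populations, SAP 6.16.1.6:** compare COVID-19 hospital days over the Evaluation Period between randomized arms in all participants, with 0 for those not hospitalized and death ranked worst, so that an early death does not count as a short stay.
- **Conditional figures:** keep the infected-only (Prevention) and hospitalized-only summaries as descriptive, without p-values.
- **Treatment populations, time to event:** leave as planned.

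The cost is SAP wording. The dates of hospital and ICU events are already recorded (Protocol 8.2.4), and SAP 6.10.3.4 already relies on attribution to COVID-19. The two time-to-event analyses exist only in the SAP. For hospital days, Protocol 9.4 requires an amendment only if a principal feature changes; redefining an exploratory analysis can be described in the SAP and study report. Sample size and the multiplicity scheme are unaffected.

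While these sections are open, one separate wording point should be reconciled: 6.16.2.4 censors participants who have been admitted, whereas 6.16.2.3 censors those who have not.
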